## ABBREVIATIONS

HP	Hydrogen Peroxide
HP13	13-Week Hydrogen Peroxide Group
HP26	26-Week Hydrogen Peroxide Group
OHI	Oral Hygiene Instruction
SRP	Scaling and Root Planing
PD	Pocket Depth
R-Rec	Relative Recession
RAL	Relative Attachment Level
BOP	Bleeding on probing
MQH	Modified Quigley-Hein Plaque Index

## ABSTRACT OF THE THESIS

Custom Application of Peroxide Gel as Adjunct to Scaling/Root planning in Treatment of Periodontitis

by

[name]

Master of Science, Graduate Program in Periodontics

Loma Linda University, September 2019

[name] [name], Chairperson

**Aim:** This study was aimed to evaluate and compare the clinical effects of scaling and root planning (SRP) combined with local delivery of 1.7% HP in customized trays to that of SRP alone.

**Materials and Methods:** Sixty patients with generalized moderate to chronic severe periodontitis will be assigned to three groups treated by SRP plus HP gel with a custom prescription tray application. The test groups will receive twice daily 1.7% HP gel in custom trays four weeks prior to SRP and will continue to application for up to 3- and 6-months post-SRP. Baseline data that is collected at the start of the study will be collected again at 4, 13, and 26 weeks post-SRP and analyzed for any changes and thus main outcome variables will include changes in pocket depth (PD), relative recession (R-Rec), relative attachment level (RAL), and changes in bleeding (BOP) using ANCOVA of main effects.

**Results:** Repeated measure ANOVA showed significant difference in pocket depth among all time points in all treatment groups. Mean BOP was significantly reduced in all groups between 4-week examination and re-evaluation with mean BOP scores at final

examination staying similar to levels at re-evaluation for HP13 and HP26 groups. Mean BOP scores at final examination group for SRP group was similar to baseline.

**Discussion:** The use of adjunctive HP in custom fabricated trays presents with no adverse effects. Significant improvement was evident in pocket depth and attachment level in both treatment groups between after 4 weeks of using the tray. No significant effect found in SRP group between baseline and 4 weeks. After SRP, significant difference was seen in all three groups between 4 weeks and 3 months.

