## CHAPTER THREE

### RESULTS

There were total 15 subjects who completed the 6-month trial. There were 10 males with an mean age of 55.6 years and 8 males with an mean age of 51.1 years. There was a total of 3 patients in SRP group, 3 patients in HP13 group, and 9 patients in HP26 group. The mean pocket depth (PD) shown in figure 1 at baseline for SRP group was  $3.88 \pm 0.06$  mm (std. error),  $4.11 \pm 0.06$  mm for HP13, and  $3.83 \pm 0.04$  mm for HP26. At the 4-week examination, PD for SRP group decreased to  $3.67 \pm 0.06$  mm,  $4.06 \pm 0.06$  mm with HP13, and  $3.55 \pm 0.04$  mm for HP26. At the re-evaluation examination, PD for SRP group was  $3.30 \pm 0.06$  mm,  $3.43 \pm 0.06$  mm for HP13, and  $3.14 \pm 0.04$  mm for HP26. The final examination, PD were  $3.43 \pm 0.06$  for SRP,  $3.40 \pm 0.06$  mm for HP 13, and  $3.23 \pm 0.04$  mm for HP26. Repeated measure ANOVA showed significant difference in pocket depth among all time points in all treatment groups. In SRP group, no significant difference between baseline and 4 weeks in pocket depth and relative attachment level.

[figure not shown]

Figure 2. Mean PD in each group, SRP, HP13, and HP26.

Figure 2 shows the mean relative recession over time. The mean relative recession at baseline was  $3.28 \pm 0.06$  mm for SRP,  $2.87 \pm 0.06$  mm for HP13, and  $3.21 \pm 0.03$  mm for HP13. At 4-weeks, it was  $3.35 \pm 0.06$  mm for SRP,  $3.23 \pm 0.05$  mm for HP13, and  $3.15 \pm 0.03$  mm for HP26. At re-evaluation it was  $3.33 \pm 0.06$  mm for SRP,  $3.27 \pm 0.05$  mm for HP13, and  $3.29 \pm 0.03$  mm for HP26.

[figure not shown]

Figure 3. Mean R-Rec in each group, SRP, HP13, and HP26.

Figure 3 shows the mean relative attachment level. The mean RAL at baseline was  $7.16 \pm 0.08$  mm for SRP,  $6.97 \pm 0.07$  mm for HP13, and  $7.04 \pm 0.04$  mm for HP26. At 4-weeks, the RAL was  $7.02 \pm 0.08$  mm for SRP,  $7.29 \pm 0.07$  mm for HP13, and  $6.69 \pm 0.05$  mm for HP26. At re-evaluation the RAL was  $6.63 \pm 0.08$  mm for SRP,  $6.15 \pm 0.07$  mm for HP13, and  $6.39 \pm 0.04$  mm for HP26. At the final exam RAL was  $6.79 \pm 0.08$  mm for SRP,  $6.71 \pm 0.07$  mm for HP13, and  $6.53 \pm 0.04$  mm for HP26.

[figure not shown]

Figure 4. Mean RAL in each group, SRP, HP13, and HP26.

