## **CHAPTER FIVE**

### **CONCLUSION**

In conclusion, the use of adjunctive HP in custom fabricated trays presents with no adverse effects. Significant improvement was evident in pocket depth and attachment level in both treatment groups between after 4 weeks of using the tray. No significant effect found in SRP group between baseline and 4 weeks. After SRP, significant difference was seen in all three groups between 4 weeks and 3 months.

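### The pocket-depth result reported for all visits in all arms is supportable at most as an overall time effect, and the summary of visit-to-visit changes stops at 3 months in a six-month trial

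*Combined protocol and SAP*

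**What the plan says.** The Abstract (Results) and Chapter Three (Results) carry the same sentence: "Repeated measure ANOVA showed significant difference in pocket depth among all time points in all treatment groups". Neither gives an F statistic, degrees of freedom, a p-value or a table of contrasts.

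Chapter Three follows it at once with: "In SRP group, no significant difference between baseline and 4 weeks in pocket depth and relative attachment level". The Abstract (Discussion) and Chapter Five (Conclusion) repeat the exception: "No significant effect found in SRP group between baseline and 4 weeks".

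The last statement on timing in the Abstract and in the Conclusion is: "After SRP, significant difference was seen in all three groups between 4 weeks and 3 months". Neither place describes PD between re-evaluation (Week 13) and the final examination (Week 26). For BOP, by contrast, the Abstract does follow the course to the final examination.

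The Introduction sets a six-month horizon for the primary objective and makes the comparison of 3 with 6 months of gel the secondary objective. The Statistical Analysis section lists PD reduction first among the primary outcomes. It specifies two-sided tests at 0.05 and names no post-hoc test or multiplicity adjustment.

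**The concern.** The time test in a repeated-measures ANOVA asks whether any visit differs from any other. The sentence is worded as if every visit differed from every other in every arm. That is a much stronger claim about a primary outcome, and the same pages state an exception to it.

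The sentence also gives no direction. A reader of the Abstract alone learns that PD differed, and that it differed between 4 weeks and 3 months. That reader cannot tell what happened in the second half of the follow-up that the primary objective covers. Weeks 13 to 26 are also the only period in which HP13 and HP26 differ by design, so the gap falls where the secondary objective has to be answered.

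**Working it through.** **Inputs.** Mean PD in mm, SEs and completers are from Chapter Three (Results).

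| Arm (completers) | Baseline | Week 4 | Week 13 | Week 26 | SE, each visit |
|---|---|---|---|---|---|
| SRP (3) | 3.88 | 3.67 | 3.30 | 3.43 | 0.06 |
| HP13 (3) | 4.11 | 4.06 | 3.43 | 3.40 | 0.06 |
| HP26 (9) | 3.83 | 3.55 | 3.14 | 3.23 | 0.04 |

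The correlation r between visits is not given. It is an assumption here, with r = 0 and r = 0.9 as the ends of the range.

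**Step 1: reproduce the reported result.** This is not possible, because no test statistic or p-value is printed. What can be checked is which reading of the sentence fits the means.

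**Step 2: text against text.** Four visits give 6 pairs per arm, 18 in all. One of them, SRP baseline to Week 4, is declared not significant by the thesis itself.

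**Step 3: pairs against the printed means.** For a change d with the same SE at both visits, z = d / (SE × √(2(1 − r))). The correlation needed for |z| > 1.96 is r = 1 − ½ × (|d| / (1.96 × SE))². For HP13, Week 13 to 26: 1 − ½ × (0.03 / (1.96 × 0.06))² = 1 − ½ × 0.2551² = 0.967.

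| Pair | d (mm) | z at r = 0 (p) | z at r = 0.9 | r needed |
|---|---|---|---|---|
| HP13, baseline to Week 4 | -0.05 | -0.59 (0.56) | -1.86 | 0.91 |
| HP13, Week 13 to 26 | -0.03 | -0.35 (0.72) | -1.12 | 0.967 |
| SRP, Week 13 to 26 | +0.13 | 1.53 (0.13) | 4.84 | 0.39 |
| HP26, Week 13 to 26 | +0.09 | 1.59 (0.11) | 5.03 | 0.34 |
| SRP, baseline to Week 4 | -0.21 | -2.47 (0.013) | -7.83 | met at r = 0 |

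The other 13 pairs exceed 1.96 in absolute value already at r = 0; the smallest is 2.83 (SRP, Week 4 to 26). If rounding of means and SE is pushed fully in favour of the claim (d larger by 0.01, SE 0.055), the two HP13 pairs still need r above 0.85 and 0.93.

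**Step 4: patients as the unit.** With n = 3 the t quantile is 4.303. A mean change of 0.03 mm is significant only if the SD of change is at most 0.03 × √3 / 4.303 = 0.012 mm.

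The printed SEs do not look like patient-level values. They would imply SDs between patients of 0.06 × √3 = 0.10 mm and 0.04 × √9 = 0.12 mm. Assuming 120 sites per patient (the 20-tooth minimum times six sites), they imply site-level SDs of about 1.1 to 1.3 mm. If they are site-level and ignore clustering, the z values above are overstated.

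**Step 5: the overall reading.** Baseline to Week 13 changes are -0.58 (SRP), -0.68 (HP13) and -0.69 mm (HP26), with |z| of 6.84, 8.01 and 12.20 at r = 0. Taking the SEs at face value, an overall time effect in each arm fits.

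**Step 6: size of the later changes.** The Week 13 to 26 rises are 0.13 / 0.58 = 22% of the Week 13 reduction in SRP and 0.09 / 0.69 = 13% in HP26. HP13 fell by a further 0.03 mm.

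**Step 7: RAL over the same period.** Printed changes are SRP 6.63 to 6.79 (+0.16), HP13 6.15 to 6.71 (+0.56) and HP26 6.39 to 6.53 mm (+0.14). The HP13 Week 13 value does not match its components: PD 3.43 + R-Rec 3.27 = 6.70 mm. With 6.70 in place of 6.15, the HP13 change would be +0.01 mm.

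**The case against.** The best defence is that a repeated-measures ANOVA is an overall test, that the sentence names it, and that Results gives the pairwise exception in the very next sentence. A general result followed by its exception is loose, but it is disclosed. This largely stands: on that reading the formal contradiction disappears. It does not rescue the wording, which does not say the test was overall, and no statistic or contrast table lets the reader find out.

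A reader might go further than the documents allow in four ways.

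- **That the means disprove significance.** They do not. The SEs belong to visit means, not paired differences, and a correlation near 0.97 cannot be excluded. For SRP baseline to Week 4 the printed means and SEs even point towards significance (z = -2.47 at r = 0); there the conflict is between two statements in the text.
- **That the later rise in PD is concealed.** Chapter Three prints mean PD with SE for every arm at all four visits. What is missing is a summary in the Abstract and Conclusion.
- **That SRP and HP26 demonstrably worsened.** The rises are 0.13 and 0.09 mm, averaged from readings in 1 mm steps, with p of about 0.13 and 0.11 at r = 0. Nothing printed shows them to be significant or clinically relevant.
- **That stopping gel did better than continuing it.** This holds for the PD point estimates only. On printed RAL, HP13 has the largest rise of the three arms, and that figure is itself doubtful. The comparison rests on 3 versus 9 patients, and continued use in HP26 is by assignment, with no compliance results reported.

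**Conclusion.** The sentence is wrong if read pair by pair and acceptable only as a statement about the overall time effect. Of 18 visit pairs, one is contradicted by the thesis's own text and two more (both HP13) need correlations above about 0.91 and 0.97. This rests on the printed SEs taken at face value and equal at the two visits. If they are site-level SEs that ignore clustering, support for the pairwise claim is weaker still, and the overall effect would also need checking with patients as the unit.

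Separately, the Abstract and Conclusion leave the Week 13 to 26 course of a primary outcome unsummarised, although the objective is six months. The changes are small and support no inference about gel duration. This is a reporting fault in a primary result that should be corrected; it is not evidence of harm or of a difference between the gel arms.

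**What to change.** - In the Abstract and Chapter Three, replace the sentence by a statement that the overall time effect was significant within each arm, if that is what was tested and it holds with patients as the unit. Give F, degrees of freedom and p.
- Report the six pairwise PD changes per arm with direction, patient-level 95% confidence intervals and multiplicity-adjusted p-values (Holm is one option). Name the pairs that are not significant.
- In the Abstract and Conclusion, give the Week 13 to 26 PD change for all three arms, described as small and not shown to be significant.
- For the secondary objective, report the HP13 minus HP26 difference in Week 13 to 26 change with a patient-level confidence interval. Within-arm contrasts, adjusted or not, do not answer that question.
- Check the HP13 Week 13 RAL of 6.15 mm against the source data before interpreting RAL over this period.

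The cost is a rerun on existing data and some rewording. The stated result becomes less favourable. The intervals will also be wide: the half-width for a mean change is 4.303 / √3 = 2.48 times the SD of change with 3 patients, against 2.306 / √9 = 0.77 times with 9.

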# CHAPTER ONE

## INTRODUCTION AND REVIEW OF THE LITERATURE

Currently, the primary non-surgical treatment for chronic periodontitis consists of supra- and subgingival plaque (biofilm) removal and mechanical debridement to reduce the periodontal bacterial load . This localized, professionally administered therapy, commonly referred to as scaling and root planing (SRP), usually results in clinical improvement and decreases the progression of the disease . SRP alone has significant limitations since studies showed that it is impossible to eliminate subgingival calculus completely and bacteria in dentin tubules . Consequently, viable bacteria that remain after SRP repopulate subgingivally, and bacteria constantly introduced into the mouth result in new biofilm formation . As a result, it is necessary to repeat mechanical debridement at least every three months during periodontal maintenance. For these reasons, numerous adjunctive treatments have been investigated and many sustained or controlled-release local delivery of antimicrobial or chemotherapeutic agents are used in the treatment of periodontitis . In addition, there are several problems and limitations associated with the adjunctive therapies for both patients and clinicians, including home care restrictions for brushing and flossing around treated sites, unsuitability for shallow pockets (<5mm), biofilm resistance to antibiotics, and etc. .

Topical hydrogen peroxide (HP) application can circumvent many of the limitations and has been shown to reduce plaque and gingival inflammation . Aqueous HP at low concentrations, which has long been used as a debriding agent and wound cleanser, also has an extensive history of topical application with SRP . Perio Protect® is a treatment

method combining mechanical and chemical debridement with 1.7% HP gel . The HP gel is directed into periodontal pockets via a custom tray, as an aid to manage biofilms better for patients with gingivitis and periodontitis. The FDA approved  $\leq 3\%$  HP gel as an oral debriding agent and an oral wound cleanser. The FDA also cleared the prescription tray branded as the Perio Tray® (Perio Protect, St. Louis, MO) as a subgingival delivery medical device in 2004 (21 C.F.R. § 872.6870). Customized extensions of the tray support the customized seal to direct the gel deep down into the sulcus or periodontal pocket and overcome the crevicular fluid flow .

Custom tray application of the HP gel as an adjunct to SRP in the treatment of chronic periodontitis has been investigated. In randomized controlled studies, it was demonstrated that significant reduction of probing depth (PD) and bleeding without mechanical intervention were seen after two weeks of HP prescription tray regimen followed by SRP and the results were maintained for up to six months with the daily use of HP prescription trays for 10 weeks . The prescription tray delivery of HP gel as an adjunctive to SRP was effective before and after full-mouth SRP in reducing PD about 1mm over SRP alone for six months in chronic periodontitis patients . However, there is currently no randomized control clinical study evaluating the differences in the duration effects of the treatment in chronic periodontitis patients with customized delivery of hydrogen peroxide gel.

The primary objectives of this randomized, controlled, single-blind, parallel clinical study are: (1) to examine if the prescription tray delivery of HP gel adjunctive to SRP results in a greater clinical improvement than SRP alone over a six-month period; and (2) to

evaluate whether the custom tray delivery of the HP gel can decrease inflammation prior to SRP.

The secondary objective is to compare if there is a difference between the length of treatment of adjunctive HP gel (3-months versus 6-months). It is hypothesized that adjunctive HP therapy will provide additional clinical benefits in PD reduction, attachment gain, and reduction of bleeding on probing (BOP) compared to SRP alone.

Null Hypotheses:

There is no significant difference between the treatment groups (SRP + HP13 vs. SRP + HP26 vs. SRP alone) with regards to reduction in PD.

There is no significant difference between the treatment groups with regards to attachment gain.

There is no significant difference between the treatment groups with regards to BOP.

## **CHAPTER TWO**

### **MATERIALS AND METHODS**

#### **Trial Design**

This study is a single-blinded, randomized, controlled, parallel clinical trial. This study has been approved by the Institutional Review Board of Loma Linda University. This protocol is written in concordance to the CONSORT 2010 statement for improving the quality of reports of randomized controlled trials.

#### **Screening and Recruitment of Participants**

A study population of sixty qualifying adults was selected by screening from patients who were referred to the Graduate Periodontics Clinic at Loma Linda University School of Dentistry. All patients received a comprehensive periodontal examination and those diagnosed generalized moderate to severe chronic periodontitis  showing minimum of one site with PD of  $\geq 5$  mm and bleeding on probing (BOP) in at least two quadrants was considered for subject recruitment. Patients who met the inclusion and exclusion criteria were eligible to participate in the study (see Eligibility and Exclusion criteria) and the patients were asked if they were willing to be a subject. Verbal and written informed consent were given to the subject outlining the purpose, timeline, as well as potential risks and benefits of participation. Once the patient accepted and was recruited as a subject they were randomized into groups by a predetermined random group assigner (see Randomization: Sequence, Allocation, and Implementation).

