## **Exclusion Criteria**

- 1) Any systemic conditions or medication intake that can alter periodontal status (e.g. uncontrolled diabetes (with <3-month recent HbA1c of  $>8.5\%$ ), anti-seizure medication, immunosuppressant, and calcium channel blockers with clinical sign of gingival overgrowth.
- 2) Immune-compromised state.

- 3) Any current heavy smoking habits (>10 cigarettes/day)
- 4) Any medical condition or history requiring prophylactic antibiotic coverage prior to dental treatment.
- 5) Females who are lactating or pregnant (as determined by medical history) or planning to become pregnant for the duration of the study.
- 7) Physical limitations/restrictions compromising oral hygiene procedures.
- 8) The presence of significant oral soft tissue pathology and/or lesions associated with ill-fitting appliances or restorations.
- 9) Tooth mobility associated with advanced periodontal disease (e.g. score of >2 using Miller Classification).
- 10) Any temporomandibular joint disorders.
- 11) Grossly carious, orthodontically banded, and third molars will not be included in the tooth count.
- 12) Presence of any significantly tipped, crowded, or largely defective restorations.
- 13) Any extreme adverse events relating to the use of HP gel (e.g. prolonged tooth hypersensitivity or aberrant soft tissue/mucosal reaction)

All participants were screened and evaluated at Loma Linda University School of Dentistry Graduate Periodontics Department. There are three groups of 20 patients, two therapy test groups and the control group.

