## **Statistical Analysis**

The primary outcome variables are PD reduction, RAL gain, and reduction in BOP. PD data was computed to provide a mean score per mouth. Secondary efficacy variables were BOP, and MQH. BOP was computed to provide a mean score per mouth for each clinical assessment and were analyzed using repeated measures (ANOVA). Outcome variable data analysis consisted of between-treatment and within-treatment (longitudinal) comparisons of PD and CAL at all examination time points using parametric procedures. Between-treatment and within-treatment comparisons employed baseline data and analysis of covariance (ANCOVA) for follow-up data. All comparisons were performed using two-sided hypothesis tests, and employed a 0.05 level of significance.

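### The Abstract and Methods state sixty patients in three groups of 20, but the Results report 15 completers (3, 3 and 9), and the claims are made without that number

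*Combined protocol and SAP*

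**What the plan says.** The size of the study is given in four places in the combined protocol and SAP.

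- Abstract, Materials and Methods (future tense): "Sixty patients with generalized moderate to chronic severe periodontitis will be assigned to three groups".
- Chapter Two, Screening and Recruitment of Participants (past tense): "A study population of sixty qualifying adults was selected by screening from patients".
- Chapter Two, closing lines of Exclusion Criteria (present tense): "There are three groups of 20 patients, two therapy test groups and the control group".
- Chapter Three, Results: "There were total 15 subjects who completed the 6-month trial", and then "There was a total of 3 patients in SRP group, 3 patients in HP13 group, and 9 patients in HP26 group".

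The Results also describe the patients by sex: "There were 10 males with an mean age of 55.6 years and 8 males with an mean age of 51.1 years". Both counts carry the same label, and they sum to 18.

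The Statistical Analysis section specifies "two-sided hypothesis tests, and employed a 0.05 level of significance", with ANCOVA and repeated-measures ANOVA as the methods. No section gives a target power, a design effect, a patient-level SD, a dropout allowance or a reason for choosing 60.

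**The concern.** A reader of the Abstract sees sixty patients, then significant changes in pocket depth and bleeding, then a statement that the trays had no adverse effects. Nothing there says that 15 patients finished. The Discussion claims a statistically significant reduction in bleeding, and the Conclusion repeats the safety and efficacy statements. Neither gives a sample size. The reader will credit these claims with the evidence of 20 patients per arm.

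Every gel-versus-SRP comparison, which is the first primary objective, has three control completers. The secondary objective, 3 against 6 months of gel, compares three completers with nine. The safety statement is affected too: if none of the 12 gel completers had an event, the one-sided 95% upper bound on the event rate would still be 22%.

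**Working it through.** **Counts.** The stated size is consistent with itself: 3 × 20 = 60. So is the completer split: 3 + 3 + 9 = 15. The two do not agree with each other, and the sex counts agree with neither: 10 + 8 = 18.

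| Group | Stated | Completed | Shortfall |
|---|---|---|---|
| SRP | 20 | 3 | 17/20 = 85% |
| HP13 | 20 | 3 | 17/20 = 85% |
| HP26 | 20 | 9 | 11/20 = 55% |
| Total | 60 | 15 | 45/60 = 75% |

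**Precision, with no assumed SD.** The standard error of a difference between two group means, in units of the patient-level SD, is √(1/n₁ + 1/n₂).

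- 20 v 20: √(1/20 + 1/20) = 0.316
- 9 v 3 (HP26 v SRP, or HP26 v HP13): √(1/9 + 1/3) = 0.667, which is 2.11 times larger
- 3 v 3 (HP13 v SRP): √(1/3 + 1/3) = 0.816, which is 2.58 times larger

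**Confidence intervals.** The 95% half-width is t(0.975, df) × SE. The planned analysis is ANOVA/ANCOVA across three groups, so for the delivered size I pool the variance over the arms. That gives 15 − 3 = 12 df before any covariate, and t = 2.179.

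- 20 v 20 (two-sample, 38 df, t = 2.024): 2.024 × 0.316 = 0.64 SD
- 9 v 3: 2.179 × 0.667 = 1.45 SD
- 3 v 3: 2.179 × 0.816 = 1.78 SD

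Pooling over three groups of 20 (57 df) would leave the first figure almost unchanged, at 0.63 SD.

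**Detectable difference (illustration).** The assumptions are 80% power, which is mine, and two-sided 0.05, which is the plan's. The difference d is solved from the noncentral t distribution with noncentrality d/SE.

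| Comparison | df | Detectable difference | Power for 0.91 SD |
|---|---|---|---|
| 20 v 20 | 38 | 0.91 SD | 80% |
| 9 v 3 | 12 | 2.04 SD | 24% |
| 3 v 3 | 12 | 2.49 SD | 18% |

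Taking each pair alone in a two-sample t-test (10 and 4 df) gives 2.07 SD and 3.07 SD. The second of these exaggerates the loss, because the planned model borrows variance from the third arm.

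**Safety bound.** With zero events in 12 patients, the one-sided 95% upper limit is 1 − 0.05^(1/12) = 0.22.

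**The case against.** The strongest reply is that sixty is plan wording left in place. The Abstract says sixty will be assigned, the Trial Design section calls the text a protocol, and the Results do disclose 15. Figure 1, the CONSORT diagram, is not visible in the extracted text and may show how many were randomized, lost and analysed. The documents also promise no power or precision, so no stated figure is shown to be wrong on that score.

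Much of this stands, and it rules out several stronger readings that a reader might infer.

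- **That a power target was missed.** None is stated. The 80% benchmark serves only to compare sizes.
- **That 45 randomized patients were lost.** The text does not say how many were randomized. Under-recruitment would mean imprecision; attrition of 85%, 85% and 55% by arm would also threaten bias. The two cannot be told apart from the text.
- **That 15 is the analysed number.** The Results say 15 completed, no analysis set is defined, and 18 people are counted by sex.
- **That the thesis claims equal effects for 3 and 6 months.** It draws no such conclusion.

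The reply does not remove the contradiction. The recruitment section says sixty were selected, in the past tense, so this is not only a plan. One sentence in the Results does not correct the Abstract or the Methods, and a flow diagram could not do so either.

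**Conclusion.** The point holds as an inconsistency in current text. The stated size is 60 in three equal groups; the reported completers number 15, split 3, 3 and 9. The Abstract, Discussion and Conclusion make their claims without the smaller number.

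The 2.1- to 2.6-fold increase in standard errors follows from the counts alone, if patients are the unit of analysis, SDs are similar across arms and the completers are the patients compared. The detectable differences of about 2.0 and 2.5 SD, against 0.91 SD at 20 v 20, also rest on the assumed 80% power and on pooling variance over three arms. If the numbers analysed differ from the completers, for instance 18 rather than 15, the figures shift. They would stay far from those of 20 per group.

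**What to change.** 1. Wherever sixty or three groups of 20 appears, including the Abstract, restate it as: planned 60 (20 per group); 15 completed (SRP 3, HP13 3, HP26 9).
2. Give the numbers randomized, lost (with reasons) and analysed in each arm, in the text as well as in the flow diagram, so that under-recruitment can be told from attrition.
3. Reconcile the 15 completers with the sex counts that sum to 18, and correct the repeated sex label.
4. Report each between-group difference with a confidence interval computed at patient level. Limit the conclusions on gel versus SRP, and on 3 versus 6 months, to what those intervals support. State the number of gel patients behind the adverse-event statement.

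The cost is wording and a little analysis. The stated size becomes less favourable. No extra enrolment is needed. Labelling the trial a pilot is optional, since the numbers and intervals carry the message.
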